TITLE: ASSESSING VENTILATOR SAFETY IN PATIENTS ON PRESSURE SUPPORT VENTILATION

Short Title: ASOP

Duke IRB # Pro00106860

ClinicalTrials.gov: NCT05125952

Clinical Protocol Synopsis

1. Title

Assessing Ventilator Safety in Patients on Pressure-support Ventilation (ASOP)

2. Background

Ventilator-induced lung injury (VILI) is known to cause significant morbidity and mortality in patients with acute respiratory failure.¹ Lung injury caused by large tidal volumes (“volutrauma”), high pressures (“barotrauma”), repetitive airway collapse (“atelectrauma”), and large changes in transpulmonary pressure during a breath (“driving pressure”) are all known to cause VILI.² Most studies on VILI have involved the effects of inappropriate (often excessive) mechanical ventilator settings. More recently, it has been noted that similar lung damage can be caused by large, patient generated, uncontrolled tidal volumes and driving pressures, which has been termed “self-induced lung injury,” or SILI^{3,4}. These patient generated large tidal volumes may be disease induced (e.g. neurologic injury) or be driven by other factors (e.g. metabolic derangements, anxiety). Importantly, interactions of patient efforts with assisted/supported modes of mechanical ventilation may worsen this.

Pressure-support ventilation (PSV) is a common mechanical ventilation mode often used in patients with active inspiratory efforts to help reduce patient inspiratory work and improve comfort. PSV effectively allows spontaneously breathing patients to determine their breath flow-rate and breath duration, eliminating flow and cycle dyssynchrony.⁵ However, pressure support ventilation does not allow for physicians to control tidal volume or driving pressure. The risk of SILI may thus be increased with PSV.

Assessing SILI risk during PSV should involve more than just measuring the delivered tidal volume and should also include the end inspiratory alveolar pressure (plateau pressure or Pplat) and the airway driving pressure (DP = Pplat-PEEP). However, these are difficult to assess during PSV. Several different methods have been proposed to address these challenges⁷⁻⁹. However, to date none of these methods have been compared to assess for concordance in their ability to indicate an increased risk of self-induced lung injury.

3. Focus of the Study and Specific Aim.

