- ix) Calculate transpulmonary driving pressure from ventilator and esophageal balloon ([a.4-a.5]-[a.1-a.3]) for each recorded breath
- x) Record P(0.1) from ventilator for 5 breaths (a.10)

b) Measure dynamic respiratory system driving pressure (DPrs-dyn) and transpulmonary driving pressure (DPtp-dyn)

- i) Record PEEP from ventilator (b.1)
- ii) Record PEEP from NM3 monitor (b.2)
- iii) Record end-expiratory esophageal pressure during a breath (b.3)
- iv) Record maximum airway pressure (b.4)
- v) Record maximum inspiratory esophageal pressure (b.5)
- vi) Record Airway plateau pressure from NM3 monitor (b.6)
- vii) Repeat for 5 total measurements of each variable
- viii) Calculate dynamic driving pressure across the respiratory system (DPrs-dyn) (b.7 = b.4-b.1)
- ix) Calculate dynamic transpulmonary driving pressure (DPtp-dyn) (b.8 = ([b.4-b.5]-[b.1-b.3]))
- x) Calculate the dynamic driving pressure across the respiratory system from the NM3 monitor DPrs-Dyn-NM3 (b.6-b.2)

c) Measure airway occlusion test (AOC)

- i) Measure PEEP (c.1)
- ii) Measure end expiratory esophageal pressure (c.2)
- iii) Perform expiratory hold
 - (1) Expiratory hold should be held for entirety of respiratory effort until airway pressure returns to baseline
 - (a) Measure maximum negative deflection of airway pressure (c.3)
 - (b) Measure maximum negative deflection of esophageal pressure (c.4)
- iv) Repeat 5 total measurements of each variable
- v) Calculate airway occlusion pressure (AOC = c.1-c.3) for each breath

d) Measure static respiratory system (DPrs-vc) and transpulmonary driving pressure (DPtp-vc) in volume control breath

- i) Change ventilator mode to SIMV (PSV+VC), with IMV breaths set in Volume control.
 - (1) Set PSV settings identical to baseline settings recorded in section 2.
 - (2) For VC breaths, volume set to average tidal volume calculated in section 2. subsection D.
 - (3) Set rate of IMV breaths to 1/min
 - (4) Set flow rate for VC breaths to minimum
- ii) Measure PEEP (d.1)
- iii) Measure end-expiratory esophageal pressure (d.2)
- iv) Measure airway plateau (d.3) during inspiratory hold
- v) Measure end-inspiratory esophageal pressure (d.4) during inspiratory hold
- vi) Repeat for 5 total measurements of each variable
- vii) Calculate respiratory system driving pressure (DPrs-vc = d.2-d.1)
- viii) Calculate transpulmonary plateau pressure (d.6 = d.2-d.4)

- ix) Calculate driving pressure across the lung ($DP_{tp-vc} = d.6 - (d.1-d.3)$)

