- e) Measure change in airway plateau pressure and patient effort with decrease in Pressure-support.
 - i) Ventilator will be returned to baseline settings
 - ii) The set pressure support will be decreased by 5 cm of H₂O (to a minimum of 5 cm of H₂O)
 - iii) The new tidal volume will be recorded (e.1)
 - iv) Measure PEEP (e.2)
 - v) Measure end-expiratory esophageal pressure (e.3)
 - vi) Perform and inspiratory hold in pressure-support
 - (1) Measure airway plateau pressure (e.4)
 - (2) Measure end-inspiratory esophageal pressure (e.5)
 - vii) Measure a P(0.1) (e.6)
 - viii) Repeat for 5 total measurements of each variable
- ix) Calculate new static respiratory system driving pressure (DP_{rs-new}) (e.7=e.4-e.2)
- x) Calculate new transpulmonary driving pressure (DP_{l-new}) (e.8=[e.4-e.5]-[e.2-e.3])
- f) Return all ventilator settings to baseline.

The order of performing these measurements will be randomized to minimize bias of the order of measurements.

All study specific measurements and maneuvers will be completed in one day. After completion of study measurements and maneuvers, the orogastric balloon will be removed.

A patient's EHR will be monitored until hospital discharge to collect previously mentioned study specific endpoints as described above.

Overall, we plan to enroll 25 patients.

10. Statistical design, analyses, sample size, and power

Statistical Design and Analysis Plan

Patient and clinical characteristics will be described overall using frequency and percent for categorical characteristics, and mean, standard deviation, median, and quartiles for continuous variables. Agreement statistics such as the intraclass correlation coefficient (ICC), Bland-Altman plots, and Cohen's kappa, will be used to assess agreement of measures between the gold-standard and the three methods of interest. A mixed-effects regression model will be used to determine the difference between each method and the gold-standard taking into account the randomization order with results presented as the least squares mean (LSM) difference with 95% confidence interval (CI). All analyses will be performed using SAS 9.4 (Cary, NC) and a p-value <0.05 will be considered statistically significant.

Sample Size and Power

This is a descriptive study. The 25-person sample size reflects the pragmatics of recruitment with available study staff and should provide adequate power to evaluate similarities given that each patient acts as his/her own control.

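### In protocol maneuver d the labels of d.2 and d.3 contradict the formulas, so as printed the volume-control driving pressure and the gold-standard transpulmonary plateau contain no airway plateau

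*Protocol*

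**What the plan says.** Maneuver d in protocol section 9 records four pressures during a volume-control breath. Step ii assigns d.1 to PEEP. Step iii reads "Measure end-expiratory esophageal pressure (d.2" and step iv reads "Measure airway plateau (d.3) during inspiratory hold". Step v assigns d.4 to end-inspiratory esophageal pressure.

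Three derived quantities follow. Step vii reads "Calculate respiratory system driving pressure (DPrs-vc = d.2-d.1", step viii reads "Calculate transpulmonary plateau pressure (d.6 = d.2-d.4", and step ix sets DPtp-vc to d.6 minus (d.1 minus d.3).

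Elsewhere the intended quantities are clear. Protocol section 2 gives "airway driving pressure (DP = Pplat-PEEP". Maneuver a uses airway plateau minus PEEP (a.4 minus a.1), and so does maneuver e (e.4 minus e.2). For the transpulmonary driving pressure, both take (airway plateau minus end-inspiratory esophageal pressure) minus (PEEP minus end-expiratory esophageal pressure). SAP section 1.3.1 computes Maneuver D from named REDCap fields, as pplat_aw_d minus peep_vent_d.

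Protocol section 9 names the transpulmonary plateau and driving pressure in volume control as the gold standard. It also states that its variable numbers match those on the research data form.

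**The concern.** Steps vii and viii put d.2 where the airway plateau belongs, but step iii has defined d.2 as an esophageal pressure. Read literally, DPrs-vc is end-expiratory esophageal pressure minus PEEP, and d.6 is the esophageal change over the breath with its sign reversed. These are different quantities from the intended ones, not imprecise versions of them.

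Step viii is the only formula in either document for the volume-control transpulmonary plateau. Protocol section 7 lists that quantity for collection, section 9 makes it the gold standard for plateau, and section 10 plans agreement statistics against the gold standard. Because the variable numbers are said to match the data form, the same ambiguity may exist on the recording sheet.

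A second, smaller exposure is the raw field pplat_aw_d. It feeds the Maneuver D ICC (SAP 1.4.2), the pairs AD, BD and CD (SAP 1.1.1 and 1.4.3) and the A-D Bland-Altman plot (SAP 1.4.4). The documents do not show which reading was entered there.

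**Working it through.** **Inputs.** Labels come from maneuver d, steps ii to v, and formulas from steps vii to ix. Write PEEP = d.1, E = end-expiratory esophageal pressure, P = airway plateau and I = end-inspiratory esophageal pressure = d.4. By the printed labels, d.2 = E and d.3 = P.

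**Algebra with the printed labels and formulas.**

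- DPrs-vc = d.2 - d.1 = E - PEEP. Intended: P - PEEP. Difference: E - P.
- d.6 = d.2 - d.4 = E - I. Intended: P - I. Difference: E - P.
- DPtp-vc = (d.2 - d.4) - (d.1 - d.3) = d.2 + d.3 - d.1 - d.4. This is symmetric in d.2 and d.3, so it equals (P - I) - (PEEP - E) whichever number holds the plateau.

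The first two results are therefore too low by d.3 - d.2. The third is right either way, so it cannot reveal the mistake.

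**Size.** The documents give no pressures, so the following values are assumed, in cmH2O.

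| | Case 1 | Case 2 | Case 3 |
|---|---|---|---|
| PEEP, E, P, I (assumed) | 8, 6, 22, 10 | 10, 13, 25, 16 | 5, 5, 20, 9 |
| DPrs-vc, printed | 6 - 8 = -2 | 13 - 10 = 3 | 5 - 5 = 0 |
| DPrs-vc, intended | 22 - 8 = 14 | 25 - 10 = 15 | 20 - 5 = 15 |
| d.6, printed | 6 - 10 = -4 | 13 - 16 = -3 | 5 - 9 = -4 |
| d.6, intended | 22 - 10 = 12 | 25 - 16 = 9 | 20 - 9 = 11 |
| DPtp-vc, printed | -4 - (8 - 22) = 10 | -3 - (10 - 25) = 12 | -4 - (5 - 20) = 11 |
| DPtp-vc, intended | 12 - (8 - 6) = 10 | 9 - (10 - 13) = 12 | 11 - (5 - 5) = 11 |
| Error, d.3 - d.2 | 16 | 12 | 15 |

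The protocol's comparison of volume-control airway plateau with the gold-standard plateau (P - d.6) would show 26, 28 and 24 instead of 10, 16 and 9.

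**Labels or formulas?** The text points both ways.

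- *For the printed labels:* NM3 readings aside, maneuvers a, b, c and e all take PEEP, then end-expiratory esophageal pressure, then an airway pressure, then a second esophageal pressure. Maneuver c matches maneuver d number for number: "Measure end expiratory esophageal pressure (c.2" and then "Measure maximum negative deflection of airway pressure (c.3". Maneuver e keeps the order, with "Measure airway plateau pressure (e.4" after the end-expiratory esophageal reading e.3.
- *For the printed formulas:* steps vii, viii and ix all become correct together if d.2 is the plateau. That is the pattern of a consistent numbering, not of scattered slips.

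**Consequence of the wrong repair, with the form's positions fixed.** If the form holds the plateau in d.2 and the formulas are edited, DPrs-vc is again -2, 3 and 0 and d.6 again -4, -3 and -4. The same happens if the form holds it in d.3 and only the labels are exchanged.

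**The case against.** The strongest reply is that the error reaches no planned SAP analysis. The SAP computes Maneuver D from fields named by content, with the correct formula, and none of its variables or aims uses d.6. SAP 1.1.1 also names Maneuver A as gold standard, so the distorted plateau comparison belongs to the protocol's plan and not to the SAP's. All of this stands, and it limits the reach. It does not make the protocol formula right, and the protocol still collects d.6 and calls it the reference.

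Second, the printed formulas give correct values if the form in fact holds the plateau in d.2. That is true. The wrong value arises when printed labels and printed formulas are followed together, which is what the protocol tells its reader to do.

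Third, nothing suggests that esophageal readings were entered in pplat_aw_d. This is fair. That part is a request for one confirmation, not a finding of error.

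Fourth, a negative transpulmonary plateau, as in all three assumed cases, or a driving pressure near zero would be conspicuous in data review. That makes the error easier to catch, but it does not say which number holds the plateau.

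Finally, the SAP describes an existing dataset (downloaded February 22, 2024; 15 patients), so what remains is a documentation correction and a check of the mapping. That is also fair, and it is why the remedy is small.

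**Conclusion.** The contradiction is real and follows from the protocol text by substitution, without any assumption. As printed, DPrs-vc and d.6 omit the airway plateau and are too low by d.3 minus d.2. That amount varies by patient, so subtracting a constant would not remove it. The figures of 16, 12 and 15 cmH2O rest on assumed pressures; the algebra does not.

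DPtp-vc, the driving-pressure half of the gold standard, is unaffected, and the SAP formula for Maneuver D is correct. Neither document shows that d.6 was stored, and no reported result is shown to be wrong. The point should be corrected because step viii is the sole definition of a quantity that the protocol treats as its reference, and because the text cannot show which repair is right.

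**What to change.** 1. Establish from the research data form and the REDCap mapping which of d.2 and d.3 holds the airway plateau. Do not decide from the protocol text alone.
2. If it is d.3, keep the labels and set DPrs-vc = d.3 - d.1, d.6 = d.3 - d.4 and DPtp-vc = d.6 - (d.1 - d.2). If it is d.2, exchange the two labels in steps iii and iv and keep the formulas.
3. Compare any stored d.6 with airway plateau minus end-inspiratory esophageal pressure, and any stored DPrs-vc with airway plateau minus PEEP. In the assumed cases both differences are -16, -12 and -15 when the derived value is wrong, and 0 when it is right. Recompute where they differ. Do not use DPtp-vc as the check, since it is the same either way.
4. In the same pass, confirm that pplat_aw_d was filled from the airway plateau reading.

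The cost is one look at the form and the mapping, two label edits or three formula edits, and recomputation of any affected derived values. Correctly identified raw readings allow full recomputation, so no new data are needed.

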15. IRB

Duke University Health System (DUHS) IRB will be utilized as the IRB of record for this project.

16. Risk-benefit assessment

The overall study is believed to be a minimal risk trial. All study maneuvers and measurements, including esophageal balloon placement, end-inspiratory holds, and end-expiratory holds, are all parts of routine clinical care. Minor discomfort may be associated with esophageal tube placement, end-inspiratory holds, and end-expiratory holds. Minor discomfort can also be associated with a breath hold used for changing ventilators. Actually changing ventilators is minimal risk, and is again common in clinical practice (i.e. patients are often placed on travel ventilators to travel to have imaging studies performed). All patients, as they will be mechanically ventilated, should be receiving or have available analgesic and/or sedating medications as part of routine clinical care that should mitigate the risk of discomfort.

Esophageal balloon placement and use can assist with ventilator management and may be used by the patients' treatment teams after study measurements are taken, which may be an indirect benefit to patients who otherwise would not have a orogastric balloon placed. Placement of the orogastric tube with an esophageal balloon rarely could cause esophageal injury. This is more often associated with long-term placement of the balloon, which will not occur in this study.

Additionally, as with any research, there is always a potential loss of confidentiality. Appropriate safeguards are in place to ensure confidentiality, as described in the RDSP. Participants' LAR can choose not to participate and continue receiving normal standard of care.

Recruitment and informed consent procedures

First, the Duke Institutional Review Board (IRB) will review and approve the study protocol before study initiation. Informed consent will be required from all participants or their legally authorized representative. Enrollment is completely voluntary.

Protections against risk

General oversight

There are several ongoing mechanisms for monitoring the occurrence of adverse events. First, all study patients will be directly monitored by trained clinical staff (either a physician, respiratory therapist, or both) during study measurements and maneuvers to assess for adverse events. After enrollment, patients' EHR will be monitored daily by study personnel, which will allow identification of any long-term adverse events associated with orogastric balloon placement.

Vulnerable populations. We will not enroll participants from vulnerable populations (e.g., imprisoned persons, minors).

17. Data & safety monitoring

Data Accuracy and Protocol Compliance.

The PI will supervise the study, including data management, data accuracy, and protocol compliance. The co-PI ([name]) will be the chief data manager and will adhere to established federal and institutional safety and protection guidelines. To assure data accuracy, the co-PI will review data reports on a routine basis. These reports will show enrollment, missing data, and other values that are neither study ID- nor outcome-based.

Adverse events (AEs), serious adverse events, (SAEs) and unanticipated problems (UPs).

It is anticipated, in this study, for AEs to be extremely rare as all interventions are part of routine clinical care and are associated with minimal risk. However, since enrolled patients will be critically ill and experiencing acute respiratory failure, it is expected that patients will have a number of unrelated adverse health events during the course of their hospital stay.

Therefore, for this study, only adverse events related to study maneuvers and measurements and long-term esophageal balloon placement will be recorded.

Adverse events related to study maneuvers and measurements will include:

- A change in respiratory status requiring increasing ventilator support (e.g., a decrease in peripheral oxygen saturation requiring an increase in ventilator FiO₂).
- Hemodynamic instability requiring addition or up-titration of vasopressors.

Adverse events related to nasogastric balloon placement will include:

- Esophageal injury
- Upper gastrointestinal bleeding

Like AEs, it is not anticipated that SAEs will occur. However, for this study, an SAE would be defined as a death related to study procedures. All serious adverse events will be reported within the standard timelines required to the IRB as appropriate and when applicable.

As the study intervention is short, it is not expected that there will be any protocol deviations. Should protocol deviations or unanticipated problems occur, they will be discussed with the PI, documented, and reported to the IRB as appropriate and when applicable.

Period and Frequency for Event Assessment and Follow-Up

Protocol deviations and other unanticipated problems, as well as AEs and SAEs, will be recorded throughout the study and reported, as appropriate, to the IRB when applicable.

The study team will record all reportable events with start dates occurring any time after informed consent is obtained until 7 (for non-serious AEs) or until hospital discharge (for SAEs).

Characteristics of an Adverse or Serious Adverse Event

To assess relationship of an event to study intervention, the following guidelines are used:

1. Related (Possible, Probable, Definite)
 1. The event is known to occur with the study intervention.
 2. There is a temporal relationship between the intervention and event onset.
 3. The event abates when the intervention is discontinued.
 4. The event reappears upon a re-challenge with the intervention.
2. Not Related (Unlikely, Not Related)
 1. There is no temporal relationship between the intervention and event onset.
 2. An alternate etiology has been established.

Expectedness

The Study PI will be responsible for determining whether an event is expected or unexpected. An event will be considered unexpected if the nature, severity, or frequency of the event is not consistent with the risk information previously described for the intervention.

Severity

The following scale will be used to grade adverse events:

1. Mild: no intervention required; no impact on activities of daily living (ADL)
2. Moderate: minimal, local, or non-invasive intervention indicated; moderate impact on ADL
3. Severe: significant symptoms requiring invasive intervention; subject seeks medical attention, needs major assistance with ADL

Reporting Procedures

Serious (fatal or life-threatening) SAEs that are unanticipated and that are related to the intervention will be reported to the IRB within 5 days of study staff's knowledge of the SAE.

Protocol Deviations and Other Unanticipated Problem Reporting

Incidents or events that meet the reporting criteria, as outlined by the Duke IRB, will be reported to the Duke IRB as needed.

The following will be included, at a minimum:

- A detailed description of the event, incident, experience, or outcome.
- A description of any changes to the protocol or other corrective actions that have been taken or are proposed in response to the unanticipated problem.

Compliance regarding Adverse Event Reporting.

The study team will be required to document and report adverse events (including serious adverse events) to the Institutional Review Board (IRB), as appropriate and in line with institutional reporting criteria.

17. Privacy, Data Storage & Confidentiality

Privacy

The study team will closely safeguard participant privacy regarding protected health and personal information. A study ID number will be generated at the time of consent and will be maintained in a secure file (e.g., linker file) which will contain the participant. Further, names, birth dates, telephone numbers, and addresses will be stored securely as described in the RDSP and only accessible by delegated study team members.

Data Storage

We will use a secure REDCap database to collect and store all study-related information. Additionally, datasets will be stored on the secured Duke server \\duhs-vclin-nc1\dusom_biostats_fs\data\BiostatsCore\CRU\Pulmonology\\ for statistical analysis.

Confidentiality

Subjects will not be identified on any study reports. University firewalls, multiple passwords, and encryption programs protect the security of the electronic data, which will be housed on a highly secure Duke University server. All personal computers are located in lockable offices and are accessible only by frequently changed passwords. The server room is accessible only to designated University Systems Administrators.

References:

5. Hess DR. Ventilator waveforms and the physiology of pressure support ventilation. *Respir Care.* 2005;50(2):166-186; discussion 183-166.

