11. Subject Participation and Duration

Study specific measurements will take one day to complete. Patients will be followed until their discharge from the hospital.

12. Study Duration

We estimate that from the time enrollment opens it will require 1 year to complete all study activities.

13. Costs to the Subject

There are no costs to participants.

14. Compensation

There is no compensation for participation in this study.

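### The protocol defines an SAE as a related death only, yet its 5-day IRB reporting rule also covers life-threatening SAEs, so a survived life-threatening event has two possible classes

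*Protocol*

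**What the plan says.** All of the conflicting text is current and sits in Protocol section 17, Data & safety monitoring.

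- **Definition** (AEs, SAEs and UPs): for this study, "an SAE would be defined as a death related to study procedures". The next sentence sends all SAEs to the IRB on its standard timelines. The balloon-related AEs listed just before are esophageal injury and upper GI bleeding.
- **Reporting rule** (Reporting Procedures): "Serious (fatal or life-threatening) SAEs that are unanticipated and that are related to the intervention will be reported to the IRB", with a limit of 5 days from staff knowledge.
- **Recording window** (Period and Frequency for Event Assessment and Follow-Up): events are recorded by start date, from consent "until 7 (for non-serious AEs) or until hospital discharge (for SAEs". No unit is shown for the 7, which may be an extraction loss.
- **Other routes to the IRB**: unanticipated problems are reported under IRB criteria as needed. The Compliance paragraph requires AEs, serious or not, to be documented and reported under institutional criteria. Neither gives a time limit.

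**The concern.** The definition and the reporting rule cannot both be applied as written. The definition admits only deaths, while the rule speaks of SAEs that are life-threatening but not fatal. Class determines both how long an event is recorded and whether a dated report is due, so the mismatch affects conduct. Two coordinators following the protocol in good faith could handle the same injured patient differently.

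At stake is the completeness and timeliness of the safety record for the most serious non-fatal harms. Both listed balloon events can be life-threatening without being fatal.

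**Working it through.** No arithmetic applies: the protocol gives no event rate, and the point rests on no sample size or power figure. The check is a comparison of the rules, followed by a worked case.

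**Step 1. Which events reach the 5-day rule?** An event must be (a) an SAE, (b) fatal or life-threatening, (c) unanticipated and (d) related.

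- If (a) means a related death, the four conditions together leave only unanticipated related deaths. The life-threatening part of (b) adds nothing.
- If (a) includes related life-threatening events, the rule also catches unanticipated, related, life-threatening events that the patient survives.

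The difference between the readings is exactly that last group.

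**Step 2. Worked case.** Take a related upper GI bleed or esophageal perforation that is life-threatening but survived.

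| | Definition governs (death only) | Reporting-rule wording governs |
|---|---|---|
| Class | Non-serious AE | SAE |
| Starts before the 7 limit | Recorded | Recorded |
| Starts after the limit, before discharge | Not recorded | Recorded |
| IRB report if unanticipated | Institutional or unanticipated-problem criteria, no time limit printed | Within 5 days |
| IRB report if anticipated | Institutional criteria, no time limit printed | Standard IRB timelines for SAEs |

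**Step 3. Can such an event be unanticipated?** I take unanticipated to mean what the Expectedness paragraph calls unexpected: not consistent in nature, severity or frequency with the risks already described. Section 16 describes esophageal injury as a rare risk without stating a severity, and does not mention upper GI bleeding. A life-threatening case of either could therefore qualify, so the group in Step 1 is not empty by construction.

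**Step 4. Does dwell time matter?** No. Section 9 states: "After completion of study measurements and maneuvers, the orogastric balloon will be removed". The class conflict holds whenever the balloon comes out.

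**Step 5. Does anything else settle the class?** No sentence gives one text priority. The top severity grade, "Severe: significant symptoms requiring invasive intervention", does not help either, because grading severity is separate from deciding seriousness.

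**The case against.** The strongest reply is that the definition is stated for this study and therefore governs, and that the reporting rule is general wording carried in from elsewhere. That is a fair reading. It still leaves a rule with words that cover nothing, and it leaves a survived life-threatening injury with no dated report, so one of the two texts needs correcting.

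Several limits on the point stand:

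- **IRB reporting is not lost.** A reader might infer that a survived event would never reach the IRB. The Compliance and unanticipated-problem paragraphs rule that out. The IRB's own timelines are not in the documents, so the real delay is unknown.
- **The window runs on onset, not discovery.** A reader might infer that any injury found late goes unrecorded. An insertion injury that starts on the measurement day and is found later can still have a start date inside the window. Events during the same-day maneuvers likewise differ between readings in reporting duty but hardly in recording.
- **The 5-day duty is narrow.** It needs the event to be both unanticipated and related, so it does not reach every survived life-threatening injury.
- **No number is supportable.** It is tempting to express the gap as a share of hospital stay or as a missed event among the patients. The first needs a unit for the 7 and a length of stay, and treats late onset as equally likely throughout the stay. The second assumes the missed event. SAP sections 1.3 and 1.4 plan no adverse-event rate or bound.
- **The minimal-risk statement is not tested against these records.** Section 16 gives it as a prior belief based on routine-care procedures, and no section plans to check it.
- **The general recording sentence is not clearly a second contradiction.** The statement that deviations and other unanticipated problems, "as well as AEs and SAEs, will be recorded throughout the study", can be read as general, with the specific windows as its detail.

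**Conclusion.** The contradiction is real and should be corrected. Under the section 17 definition, a related life-threatening event that the patient survives is non-serious. Under the section 17 reporting rule, it is serious. The practical differences are a longer recording window for events that start after the 7 limit and, for events that are also unanticipated, a 5-day report.

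The affected group is small in concept, and section 17 expects AEs to be extremely rare. No numerical magnitude is claimed. The agreement analyses in Protocol section 10 and the SAP do not depend on the point.

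The conclusion assumes that unanticipated and unexpected mean the same thing. The difference in recording window also assumes that the 7 limit falls before discharge, which cannot be confirmed without its unit. The difference in class and reporting duty needs neither the unit nor any length of stay.

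**What to change.** In section 17, define an SAE for this study as an event related to study procedures that is fatal or life-threatening. The existing window to discharge and the existing 5-day rule then apply to it without further change. Confirm that the unit of the 7 limit is printed in the source document, and add it if it is not.

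Deleting the life-threatening wording from the reporting rule would also remove the contradiction. It is the weaker choice, because survived life-threatening injuries would still have no dated report.

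The cost is a one-line protocol amendment. Surveillance is already in place: section 11 says "Patients will be followed until their discharge from the hospital", and section 16 plans daily EHR review, "which will allow identification of any long-term adverse events associated with orogastric balloon placement". Recording every balloon injury to discharge whatever its seriousness would be a separate preference and is not needed here.

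The SAP cites a data version dated February 22, 2024 and 15 enrolled patients (sections 1.2.3 and 1.4.2), so measurements may already be complete. If so, state in the safety report which definition was applied. If it was the narrow one, check the records for survived life-threatening events.
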